7.4 Study progress reports.....	13
7.5 Stopping rules	14
8. Record keeping and data management.....	14
9. Statistical analyses and data handling	14
10. Dissemination of Results and Publications	15

1. Study Summary

To assess the effectiveness, feasibility and acceptability of an Acceptance and Commitment Therapy (ACT) based psychological intervention delivered in a group format by a qualified psychologist on psychological measures (distress, psychological flexibility, Health-related Quality of Life (HRQOL)), and medical outcomes (described in section 6) when compared to a control group who will receive treatment as usual (TAU) within a patient group with a diagnosis of Gastrointestinal Dysmotility (GID). A further description of the results of those with Chronic intestinal pseudo-obstruction (CIPO) against those non-CIPO will also be included to see whether the preliminary effectiveness or needs differ between these two groups.

The ACT intervention will be carried out in an online format and consist of 7 weekly sessions followed by an 8-week follow up with each session lasting approximately 120 minutes. An online format will be utilised due to the logistics – an online format will allow all participants to attend, taking into consideration the COVID pandemic and geographical location of patients in our service being a national centre for patients needing home parenteral nutrition (HPN). All patients will be followed up and asked to complete feedback forms after each session to assess effective components of the intervention. A subset of patients will also be invited to take part in a qualitative interview based on their experiences of the intervention. Patient experts from the Pseudo Obstruction Research Trust (PORT) and our patient focus group will be invited to be involved in aspects of the study such as the study design, development of the therapeutic manual, recruitment, and dissemination of the study's results.

At the time of writing and to our knowledge this will be the first study to assess whether a group psychological intervention is effective using a standardised therapeutic manual adapted to those diagnosed with GID. Moreover, it looks at whether delivering psychological interventions in an online format in a group setting is acceptable and feasible with this patient population and in the NHS environment. Outcomes from this study will not only shape future psychological interventions but also promote psychological support for this cohort of patients who have expressed wanting this service. If group interventions are proven to be effective, it will mean that patients may have more rapid access to psychological intervention rather than inevitable long waiting lists for individualised psychological support. In addition, the group intervention can be adapted for further gastrointestinal conditions in the future.

2. Project Team

2.3 Funding

We achieved external funding from PORT/Bowel Research UK. This is a £49, 994.20 grant over 18 months. There will be no further funding to cover the cost of this study.

2.4 Organisational Structure and Responsibilities

Chief Investigator:

Design and conduct of study
Preparation of protocol and revisions
Recruitment of participants
Organising study meetings
Reviewing progress of the study and agreeing to changes in the protocol if necessary
Oversight of patient safety by conducting regular meetings with study team
Publication of study reports
Study budget holder
Responsible for data management plan

Sub-investigator:

- Design and conduct of study
- Preparation of protocol and revisions
- Recruitment of participants
- Organising study meetings
- Reviewing progress of the study and agreeing to changes in the protocol if necessary
- Oversight of patient safety by conducting regular meetings with study team
- Publication of study reports
- Study budget holder
- Responsible for data management plan

3. Background Information and Rationale

Gastrointestinal dysmotility (GID) has no universally accepted definition but it is a broad term that encompasses a spectrum of disorders where there is dysregulation or disruption of the complex enteric neuromuscular co-ordination necessary for motility of food through the gastrointestinal tract [1, 2]. At the severe end of the spectrum, disruption to GID can lead to intractable gastrointestinal symptoms (pain, cramps, bloating, difficulty maintaining weight, constipation, diarrhoea, nausea, vomiting, malnutrition) [1,2], and is a recognised cause of people needing long term home intravenous feeding, known as home parenteral nutrition (HPN) [1-6]. GID can be separated into sub-types of Chronic intestinal pseudo-obstruction (CIPO) and non-CIPO; the latter is characterised by symptoms representative of intestinal occlusion despite no physical obstruction being present. A study found that the CIPO sub-type of GID is associated with higher HPN dependency, higher incidence of bacterial overgrowth and more surgical intervention compared to those with a non-CIPO sub-type of GID [7].

It has been found that the quality of life (QOL) and psychological wellbeing of those diagnosed with a GID is impacted due to the management of gastrointestinal symptoms and treatment for maintaining nutrition and body weight [8]. There is significant evidence detailing the effect of GID and, where required, HPN on daily life and psychosocial outcomes due to the inability to eat normally, loss of independence, lifestyle change and control of bodily functions [9-11] with many experiencing a difficult journey from symptom onset to getting a diagnosis of GID, which impacted upon their psychological wellbeing along the way [12].

A recent study reported that there is increasing awareness of the psychological impact of severe GID diagnoses and the roles of psychosocial support, with clinical psychologists becoming an integrated part of the multidisciplinary care for these patients [13]. Vasant et al [14] surveyed clinicians' perspectives on the management of patient's diagnosed with severe GID and found that clinicians felt that psychological therapies were the second most useful intervention after treatment for bacterial overgrowth. Studies in other gastrointestinal conditions have used various psychological interventions including gut hypnotherapy [15], mindfulness [16], cognitive behaviour therapy (CBT) [17], and solution focussed therapy [18] with mixed effects on psychological, QOL and medical outcomes. However, there is little to no data on what type of therapeutic modality or more so what component of the psychological intervention is most effective in the GID population.

Recently a study found that an Acceptance and Commitment Therapy (ACT) intervention was effective in reducing psychological distress in those diagnosed with IBD [19]. ACT has also been found to be beneficial for psychological wellbeing in many other chronic conditions [20] and works on the principle

that rather than try to modify or eliminate negative thoughts or feelings, it encourages individuals to accept that adverse experiences exist whilst simultaneously fostering a commitment to move toward values that have been identified and adopted by the individual [21].

4. Aims of the proposed research

4.1 Primary Objective:

To assess the effectiveness, feasibility and acceptability of an online ACT based psychological intervention on psychological measures (distress, psychological flexibility, QOL and medical outcomes (described below in section 6) when compared to a control group who will receive treatment as usual (TAU).

4.2 Secondary Objective:

The study aims to recruit people with a diagnosis of GID, with a description of the results of those with CIPO against those non-CIPO to see whether the effectiveness or needs differ between these two groups.

5. Study Design

This study will be a pilot randomised controlled trial (RCT) with patients diagnosed with gastrointestinal dysmotility. Assessment of QoL of intestinal failure (IF) patients is very complex as IF is not only affected by the HPN treatment itself but also by the underlying disease and frequency of hospital readmissions. Therefore, a range of data will be collected including demographic characteristics, psychological outcomes, and medical outcomes, collected at different timepoints to allow for analysis (further detail is provided section 7.6 below).

Blinding of investigators or participants will not be possible in this study as participants and investigators will know whether participants had been allocated to the group or not. Participants allocated to the group intervention will be put into a group of 9-10 people. There will be maximum five rounds of the group intervention over the study period to meet sample size. The intervention is adapted from the Better Living with Illness group protocol [22] based on ACT. The group will be delivered over 7 weeks in weekly two-hour sessions, with a follow up 'reunion' at 8 weeks. A treatment manual has been adapted by the chief investigator who has received specialist training in ACT and previous experience of running this intervention online to people with long-term conditions. Each session utilises experiential exercises and metaphors to cover core ACT processes. Worksheets and guided mindfulness meditation exercises will be recommended to facilitate learning and encourage home practice. The intervention also covers problem solving skills, pacing, assertiveness skills and goal setting as they are important features of living with a long-term condition such as GID. An overview of the content of group sessions is provided in figure 1.

Figure 1, Session content of group

Attendance will be recorded to assess recruitment and retention for the acceptability and feasibility part of the study and all group participants will be asked to complete a feedback form for each session attended of the intervention to assess effective components. Feedback will not be incorporated as the study progresses to retain intervention consistency for each participant as close as possible.

The study will utilise a mixed-methods design using quantitative standardised psychometric questionnaires to address psychological and quality of life outcomes, as well as a qualitative approach. The study will use face-to-face or telephone semi-structured interviews to explore participants experiences and views on the feasibility and acceptability of the intervention. These interviews will take place at one time point after the group intervention.

6. Detailed Plan of Investigation

6.1 Recruitment procedure

The proposed recruitment strategy will involve screening the database at Salford Royal Hospital, Northern Care Alliance NHS Foundation Trust (NCAFT) for potentially eligible patients with gastrointestinal dysmotility. This search will be conducted by the research team working on the study and subsequently participants that fit the eligibility criteria will be sent a letter, approved by ethics, introducing them to the study and outlining what would be involved. Participants may also be approached during their HPN clinic appointment. A follow-up courtesy call 2-3 weeks after sending the letter may also be made by a member of the research team.

A telephone screening assessment will then be arranged with all interested participants for the therapeutic group programme to assess for suitability, to conduct a brief psychological assessment and check they meet inclusion criteria. During this phone call the research study will be discussed including the rationale in line with details provided on the participant information sheet and patients will have the opportunity to ask questions.

If after this telephone screening assessment with a clinical team member they meet inclusion criteria, and wish to continue, the research team will arrange a convenient time to obtain informed consent, via a consent form. Participants will be given a minimum of 24 hours to decide whether or not to take part. In some circumstances the participant may be asked to complete consent over the telephone. For example, in situations where to protect the safety of the participant and staff, it is not appropriate to bring the participant into a clinical setting for the consent process (e.g. during the COVID-19 pandemic). Participants will be randomised (using random number sequence methods) into one of two groups; the ACT intervention programme, or a control group receiving treatment as usual where they will not receive the psychological intervention during the study. Letters will be sent to GPs of all patients taking part in the study.

Those who do not give consent to be included in the study will still be able to access the Intestinal Failure Psychology team and standard NHS care and resources.

All participants who provide consent will be asked to complete questionnaires at 3 timepoints (T1- baseline/pre-treatment; T2- week 7/post-treatment & T3 – 8 week-follow-up). These will be completed via paper, online, over the phone or email. The questionnaires will not have personal identifiable information on them but will be pseudonymised with a study participant number, of which only members of research team will have access to.

The second part of the study will involve semi-structured interviews performed by a suitably qualified member of the research team with training or experience to perform qualitative interviews. For the qualitative element of the study, participants will be able to register interest in the qualitative study and receive additional information about this part. Interviews will be conducted at a mutually agreeable time between the moderator conducting the interviews and the participant. If possible, they will try to accommodate this with their routine appointments at Salford Royal Hospital to make it easier for the participant to take part or alternatively over a video consultation.

6.2 Inclusion Criteria:

- 1) Has a diagnosis of Gastrointestinal Dysmotility
- 2) Age 18 years or above
- 3) Is fluent in English

6.3 Exclusion Criteria:

The participant may not enter the study if ANY of the following apply:

- 1) Insufficiently well to give consent or to take part
- 2) Currently receiving or due to start psychological therapy at another service or privately
- 3) Difficulties such that they are currently in receipt of on-going input from secondary care mental health services.
- 4) Substantial substance abuse difficulties
- 5) Severe and/or chronic mental health problems such as personality disorders where the interpersonal difficulties themselves are the required focus of an intervention
- 6) A learning disability, at such a level that specialist skills would be required to deliver an intervention.

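### Section 6.1 states no stratification by CIPO status, although CIPO versus non-CIPO is the only secondary objective: a modest weakness that is cheap to remove before allocation

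*Protocol*

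**What the plan says.** Section 6.1 gives the allocation method as "Participants will be randomised (using random number sequence methods) into one of two groups". It mentions no strata, blocks, minimisation or ratio, and neither does any other section.

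Section 4.2 contains one secondary objective, which is to recruit GID patients and report by subtype: "with a description of the results of those with CIPO against those non-CIPO to see whether the effectiveness or needs differ". Section 9 repeats this as a described subgroup comparison and states no interaction test.

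Section 3 reports an earlier study in which "the CIPO sub-type of GID is associated with higher HPN dependency, higher incidence of bacterial overgrowth and more surgical intervention". Section 6.8 lists gastrointestinal/HPN complications, HPN requirements and hospital readmissions among the medical outcomes.

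Section 9 plans an ANCOVA adjusted for baseline scores for all psychometric measures. The only analysis it states for the medical outcomes is descriptive.

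On size, section 5 says "Participants allocated to the group intervention will be put into a group of 9-10 people" and "There will be maximum five rounds of the group intervention over the study period to meet sample size". No total, allocation ratio or CIPO share is stated.

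**The concern.** Whether effectiveness differs by subtype can only be described if each subtype has patients in both arms. The stated method leaves the division of CIPO patients between ACT and TAU to chance, and the fewer there are, the more uneven that division can be. An analysis plan can add a covariate later, but it cannot move patients between arms, so the time to act is before allocation.

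There is a second, smaller effect on the main comparison. If the arms differ in their share of CIPO patients, a characteristic that the protocol itself links to HPN dependency and surgery is unequally distributed. This matters most for the medical outcomes, for which no adjusted analysis is stated.

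**Working it through.** The protocol has no figure to reproduce here, so the check measures how often a poor split would occur and what it would cost.

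**Inputs**
- Intervention arm, from section 5: at most 5 × 9 = 45 to 5 × 10 = 50 patients.
- Total: 90 to 100, assuming 1:1 allocation (ratio not stated).
- Number of CIPO patients, m: not stated; assumed range 10 to 30.

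**1. Chance of a 2:1 or worse split, each patient allocated independently**

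With X ~ Binomial(m, 0.5), the chance is 2 × P(X ≥ r), where r is the smallest count at least twice the remainder.

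| m | mildest split that counts | independent allocation | arm totals fixed at 1:1 (N = 90 to 100) |
|---|---|---|---|
| 10 | 7/3 | 34.4% | about 31% |
| 14 | 10/4 | 18.0% | 14-15% |
| 20 | 14/6 | 11.5% | 7-8% |
| 30 | 20/10 | 9.9% | 4-5% |

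The last column uses the hypergeometric distribution. It covers the case where arm sizes are held equal without stratifying. The risk falls but does not disappear.

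**2. Cost of a poor split within the subgroup**

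If one arm holds a share s of the subgroup, the standard error of the ACT-TAU difference rises by the factor √(0.25 / (s(1 − s))).
- 60/40: √(0.25/0.24) = 1.02
- 2:1: √(0.25/0.2222) = 1.06
- 70/30 (that is, 7/3 or 14/6): √(0.25/0.21) = 1.09

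**3. Comparison with the effect of subgroup size**

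For m = 20 split 10/10, the standard error is √(1/10 + 1/10) = 0.447 SD. The difference detectable with 80% power at two-sided 5% is (1.96 + 0.84) × 0.447 ≈ 1.25 SD. With a 70/30 split it is 1.37 SD. The subgroup is imprecise even when perfectly balanced.

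**4. Imbalance in the overall comparison**

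The SD of the between-arm difference in CIPO share is √(4p(1 − p)/N). With N = 90:
- m = 10 (p = 0.111): SD = 0.066; chance of a difference above 10 percentage points about 13%.
- m = 30 (p = 0.333): SD = 0.099; chance about 31%.

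These are normal approximations with independent allocation. If subtype shifted an outcome by 0.5 SD after adjustment (assumed), a 10-point difference would move the contrast by 0.10 × 0.5 = 0.05 SD. The unadjusted standard error of that contrast is √(4/90) = 0.21 SD.

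**5. After stratification**

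With permuted blocks of 4 within each subtype (block size illustrative), the arms differ by at most 2 per subtype: 11/9 at worst for m = 20. The standard-error penalty is then √(0.25/(0.55 × 0.45)) − 1 ≈ 0.5%.

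**The case against.** The strongest case against is that this is a pilot, that the secondary objective is worded as a description covering needs as well as effectiveness, and that describing needs does not require balanced arms. A 2:1 split costs only 6% in standard error, and subgroup size is the real limit. Covariate choice is commonly left to an analysis plan, which is not shown here. All of this stands, and it makes the point a cheap improvement rather than an error. It does not remove the point, because effectiveness is part of the objective and stratification cannot be added after allocation.

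A reader might also infer stronger claims that the protocol does not support:
- That simple randomisation is specified. The text says that random number sequences are used and is silent on blocks and strata.
- That the protocol calls CIPO the more severe subtype, or the smaller one. It reports an association with three features and gives no CIPO share.
- That CIPO patients could easily fall almost wholly in one arm. Under independent allocation, a 90/10 or worse split has a chance of about 2.1% for m = 10 and 0.04% for m = 20.
- That the overall comparison is biased. Chance imbalance affects the sample obtained; randomisation remains unbiased on average. The medical outcomes are also recorded at baseline, so an imbalance in them can be seen.

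**Conclusion.** The point holds as a modest design weakness. No stratification by CIPO status is stated, although subtype is the subject of the only secondary objective and is presented as related to the trial's medical outcomes. An uneven split is a material possibility if CIPO patients number about 10 to 20 (about 34% down to 11.5%, or 31% down to 7-8% with fixed arm totals), and has a chance of 10% or less at 30. The consequence is about 6% on the within-subgroup standard error at 2:1 and 9% at 70/30, plus some chance imbalance overall.

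These figures rest on assumed 1:1 allocation and an assumed CIPO count; those for fixed totals and for overall imbalance also rest on a total of 90 to 100, inferred from the maximum number of rounds.

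**What to change.** In section 6.1, state that allocation is stratified by CIPO/non-CIPO status, taken from the medical record before allocation. Apply the strata across the whole trial: up to five rounds by two subtypes would leave as few as 10/5 = 2 CIPO patients per round at the low end of the assumed range. State the allocation ratio, and choose a block size or equivalent method that still lets ACT groups of 9-10 be formed. In section 9, add CIPO status to the baseline-adjusted ANCOVA.

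The cost is small. Subtype must be confirmed before allocation, at a centre that already screens its own database for these patients, and the model uses one further degree of freedom. The report should still present the subgroup results as imprecise, because stratification evens the split without adding patients.

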6.4 Screening for eligibility

As per current clinical practice within a psychology service, a telephone assessment will be conducted by the assistant psychologist or qualified psychologist (both members of the research team), with all participants to screen for eligibility to ensure that the person meets the inclusion/ exclusion criteria, and equally importantly to conduct a brief psychological assessment. A screening tool is not used but decisions are based on clinical judgement (as is clinical practice) owing to answers given to questions about their condition, an assessment of risk, expectations and goals and level of commitment/engagement. This assessment means we will be well placed to judge whether our intervention is suitable, and we can sign post and inform GPs if other services are better placed to meet potential participants' needs. We will of course, in line with good clinical practice, continue to monitor participants' needs throughout the course of the intervention.

6.5 Ineligible and non-recruited participants

People who are ineligible or not recruited will have access to the existing array of NHS services.

6.6 Study duration

The proposed project duration is expected to be 18 months from first receiving funding from PORT and Bowel Research UK. The start date for the study will be as soon as ethics and local C&C has been granted. The ACT intervention will occur in total over a 15-week period (7 weekly sessions plus an 8 week-follow up) with each session lasting approximately 120 minutes and it is expected to take between 25 minutes to complete the questionnaires. The final study visit for the group intervention

will be 31/05/2022. The qualitative interview phase of the study is expected to take participants between 30-60 minutes and interviews will be conducted once a participant has completed the intervention. All interviews will be conducted by October 2023. Writing up the results of this study is expected to be complete within 12 months after study end. Approximate end date 31/10/2023. Following this no further data collection will take place i.e. the last patient will have completed their last visit.

